**Figure 3a. Change in CVD risk factors**

**Figure 3b. Percent change in exercise capacity**

ease of use, **d)** appropriate and completeness of content, and **e)** overall patient and staff satisfaction. From the patient centered outcomes perspective, our web analytics and patient-facing survey data demonstrated that 67% of patients used the mHealth platform on a daily basis with an additional 22% using it multiple times per week. From the patient surveys, 72% of patients reported using the platform for its content and ability to record activities (daily agenda, graphs and diary). With this, 67% of patients were “satisfied” or “extremely satisfied” with the educational content provided; 78% felt the platform helped them to “better understand their health”; 89% reported the platform gave them “better control of their health”; and 89% also reported that the platform “increased their motivation to work on healthy lifestyle choices”. **Figure 3a** shows the percent change from baseline to the end of CR ( $32 \pm 3$  CR sessions) for body weight (kg), body mass index (BMI-kg/m^2), systolic blood pressure (mmHg), total cholesterol (mg/dL), low density lipoprotein cholesterol (LDL-mg/dL), and triglycerides (mg/dL) where CON represents patients enrolled in conventional center-based CR and CON+ represents patients enrolled in conventional center-based CR with the addition of mHealth platform. **Figure 3b** shows the percent change in volume of oxygen consumed during a maximal cardiopulmonary exercise test (VO2 peak), percent of age and sex predicted VO2 peak (VO2 %predicted), and functional aerobic capacity as a percentage of age and sex predicted (FAC). Data are reported as mean $\pm$ sd (\*denotes statistically significant within group change). While pilot in nature and with a sample size of n=10 per group, these data clearly demonstrate the potential of a mHealth platform to augment conventional center-based CR.

[figure not shown]
Our data are in line with recently published studies examining the impact of various types of telerehabilitation technologies on health outcomes in CR patients. For example, Frederix and colleagues compared conventional center-based CR to conventional center-based CR plus weekly email or SMS text messaging (“telerehabilitation”) which provided feedback on patients pedometer based physical activity monitor. Despite the relatively limited intervention, these authors demonstrated a significant increase in exercise capacity (peak oxygen consumption) at the end of the intervention compared to the control group. Further, these authors demonstrated a trend towards reduced hospitalizations for patients in the telemonitoring group. Additionally, Avila et al. examined the impact of an exercise-based rehabilitation program between conventional center-based CR and home-based CR using weekly feedback via telephone or email to the home-based CR patients. The contact moments with the home-based CR patients provided the opportunity to check for adverse events, provide feedback on exercise performed during the week, discuss the exercise program components, and discuss adherence and barriers when necessary. Again, despite the relatively limited “mHealth” intervention, these authors demonstrated a significant improvement in exercise capacity (peak oxygen consumption) in the home-based CR patients. In a more comprehensive approach but with a much smaller sample size and shorter duration, Widmer and colleagues demonstrated that the addition of a digital health intervention significantly improved specific CVD risk factors while reducing 3-month rehospitalizations.

In light of previous studies, our protocol development activities formed the basis for the development of the comprehensive study protocol highlighted below. Our development process was and continues to be informed by patient feedback to ensure findings of this research are applicable to patients faced with the decision of whether to participate in CR. Our study protocol will be posted to clinicaltrials.gov prior to patient accrual.

### 3.3 Study Design

To address our specific aims we will use a single-center, prospective, three-arm, parallel group, randomized controlled trial design (**Figure 4**). At the time of identification of eligibility for participation (See below: Patient Population), patients will be randomized to one of three arms (1:1:1 ratio): **Arm 1** consists of patients randomized to conventional CR only (CON), **Arm 2** consists of patients randomized to conventional CR with the addition of the mHealth platform (CON+), and **Arm 3** consists of patients randomized to remote case management using the mHealth platform only (HOM+). Clinical metrics will include traditional cardiovascular risk factors with additional tracking of service utilization and adherence, and quality

**Figure 4. Study Design Outline**

of life. Measures will be made at baseline (pre-intervention) and ~3-months (coinciding with completion of conventional CR). Additional follow-up will occur at 12 months post CR entry. Randomization to study arms will be done with a multidimensional dynamic allocation algorithm, minimizing imbalances in age, sex, body mass index, and race across study arms.

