### **3.4 Participant Recruitment**

*[[Male and Female patients, aged 18-80 years, who are identified as eligible for conventional CR will be recruited from the Mayo Clinic Health System (MCHS) (or our subcontract site University of Minnesota Medical Center [M Physicians/Fairview Health System]) by clinical research coordinators, referring physicians, and/or CR staff. We will make every attempt to recruit equal numbers of both men and women and appropriate distribution of minority participants.]]*

Inclusion Criteria: Patients must own, or have reliable access to, a smartphone or desktop computer with internet access, and an e-mail address. Eligible patients will have a history of one of the following: acute myocardial infarction/acute coronary syndrome, stable angina pectoris, percutaneous coronary intervention, or heart failure. Additionally, patients who underwent a surgical procedure which includes an indication for cardiac rehabilitation (coronary artery bypass surgery, heart valve repair/replacement, or heart transplant) will be enrolled but will only complete 6-minute walk test for measurement of exercise capacity per clinical practice guidelines.

Exclusion Criteria: Patients referred to CR with ventricular assist devices are not eligible. Patients who do not own, or have access to, a smartphone or desktop computer with internet access will not be recruited. Patient unable/unwilling to provide informed consent will not be enrolled.

The annual population of eligible CR patients at Mayo Clinic varies by diagnosis. As highlighted by Ades and colleagues report an annual nation-wide incidence of ~1,963,000 myocardial infarction, percutaneous coronary intervention, and systolic heart failure patients eligible for CR compared to only 395,000 coronary artery bypass surgery patients. While this list is clearly not inclusive of all eligible referral diagnoses, it provides an illustration of the disproportionate number of surgical vs. non-surgical patients eligible for CR. Importantly, despite the significantly larger number of non-surgical patients eligible for CR, it has been reported that CABG patients demonstrate higher rates of participation in CR^43.

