*[[Mayo Clinic has developed an in-house referral protocol for all patients meeting CR eligibility guidelines. Specifically, all patients visiting the clinic and/or hospital for one of the above inclusion criteria can be identified by our research team through the medical records, screened for eligibility, and approached to determine interest/willingness to participate in the study. This approach will maximize our potential to identify eligible individuals for screening and all patients who meet all eligibility criteria will be asked to participate. In 2018, the Rochester, MN CR program provided services for 459 new patients. Of those patients 68 were self-identified minority race or ethnicity (~15%) and 157 were women (~34%). Moreover, 365 patients were referred for non-surgical indications (~80%) which would meet the inclusion criteria of this proposal. Additionally, we have enlisted the assistance of an additional site in the Minneapolis/St. Paul metropolitan area (Hennepin County). The University of Minnesota Medical Center (M Physicians/Fairview) health network has 10 cardiac rehabilitation locations which provide cardiac rehabilitation services to ~4,000 new patients annually. Of these patients, ~3,000 receive their services within the Minneapolis/St. Paul urban area, many of which are from diverse racial and ethnic backgrounds.]]* We will maximize our retention by providing participants with remuneration for their time in the research program. This will include \$50 for the baseline visit, \$50 for the first follow-up visit at the end of the intervention, and \$50 for the final follow-up visit at 1-year post event. Payments will be made at the time the participant completes the final follow-up visit or informs a study team member of their desire to withdraw from the study.

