**Physical Activity:** Self-reported physical activity levels will be assessed using the International Physical Activity Questionnaire (IPAQ) and the Duke Activity Status Index (DASI). These activity questionnaire quantify participant's activity patterns in categories of vigorous, moderate, and leisure. This will be measured during the week immediately prior to beginning study arm activities and during each of the two follow-up study visits.

**Exercise Capacity:** Exercise capacity will be measured by the following standard metrics: 1) six-minute walk test (6MWT), 2) a standard 12-lead ECG monitored symptom-limited exercise stress test or cardiopulmonary exercise test to include measurement of oxygen consumption (CPET). The CPET will be the preferred measure of exercise capacity as measurement of peak oxygen consumption ( $\text{VO}_{2\text{peak}}$ ) is considered the Gold standard measure of fitness. For standardization, the 6MWT will provide absolute distance walked and percent of age predicted distance walked as a universally accepted assessment of exercise capacity. The CPET will be conducted in the Mayo Clinic Integrated Stress Center as standard clinical protocol. These measures of exercise capacity will be conducted at the time of enrollment in the research program and during each of the two follow-up study visits.

**Dietary Patterns:** Dietary pattern will be obtained using a standard food frequency questionnaire at the time of enrollment and during each of the two follow-up study visits.

**Quality of Life:** Physical and mental health-related quality of life will be assessed using the validated 9-item Patient Health Questionnaire (PHQ-9) and the validated Dartmouth 9-item Short-Form health survey at the time of enrollment and each of the two follow-up study visits.

**mHealth Remote CR Case Management Platform:** *The mHealth remote case management platform developed specifically for CR is an asynchronous platform consisting of several services intended to empower patients by raising their awareness about their health condition. These services give patients the opportunity to better understand, manage, and control their health condition for an improved quality of life.*

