### **3.8 Potential Limitations and Alternative Strategies**

We acknowledge there may be potential limitations to our approach. First, by only including non-surgical CR eligible patients we are limiting the generalizability of our findings to the non-surgical population studied. However, we recognize that the number of non-surgical eligible CR patients is significantly greater than the number of surgical patients typically enrolled in CR and that surgical patients (e.g. CABG) already have higher rates of CR participation. Counterintuitively, this has a potential benefit in that it opens additional lines for future research examining the predictors of referral, enrollment, participation, and completion of CR programs among surgical vs. non-surgical patients. Secondly, there is sparse data available on the ability of mHealth to improve patient-centered outcomes such as mortality. While we will plan to follow our enrolled participants for one-year in an effort to examine the impact of mHealth on this important patient-centric outcome, we recognize that the number of patients who suffer fatal cardiac or non-cardiac events will likely be relatively small. In an attempt to collect meaningful patient-centric data, our primary outcome for Aim 3 will be rehospitalization over this same time period. *[[Lastly, although the population of patients of African descent has increased substantially over the past few years in our community, we recognize the relatively homogeneous nature of the predominately Caucasian Olmstead County population. We have engaged directly with the Center for Health Equity and Community Engagement Research within the Office of Health Disparities Research to develop dedicated strategies to maximize our recruitment of minority populations and overcome this potential limitation to ensure appropriate representation. We have also added a co-Investigator with extensive experience working with African American research participants. Moreover, we have engaged with University of Minnesota Medical Center (Minneapolis/St. Paul urban area) to assist with additional recruitment of African American patients as needed. By partnering with this additional site, we will increase the pool of eligible minority patients located outside the confines of Olmsted County. Further, we will employ a multidimensional dynamic minimization algorithm to minimize imbalances between groups and ensure that the distribution of both women and minorities are appropriately distributed across all cohort arms of the study.]]*

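### A second site recruits, but site is neither an allocation factor nor a term in the Aim 2 model, which leaves a modest, avoidable chance imbalance between arms

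*Combined protocol and SAP*

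**What the plan says.** **Design label.** Section 3.3 states a "single-center, prospective, three-arm, parallel group, randomized controlled trial design", with patients allocated 1:1:1.

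**Recruitment.** Section 3.4 names as a source of patients, besides Mayo, "our subcontract site University of Minnesota Medical Center". It adds that this "health network has 10 cardiac rehabilitation locations which provide cardiac rehabilitation services to ~4,000 new patients annually"; the Rochester programme served 459 new patients in 2018. Section 3.8 gives the purpose of the partnership: "to assist with additional recruitment of African American patients as needed".

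**Allocation.** The text at Figure 4 describes a dynamic algorithm "minimizing imbalances in age, sex, body mass index, and race across study arms". Section 3.7 describes the same kind of minimisation and speaks only of women and minorities. Neither names site.

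**Primary model for Aim 2.** Section 3.7 compares three-month VO2peak between pairs of arms by ANCOVA, with baseline VO2peak as the only stated covariate. The non-inferiority margin for HOM+ against CON is 2.8 mL/min/kg.

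**Measurement.** Section 3.5 says: "The CPET will be conducted in the Mayo Clinic Integrated Stress Center as standard clinical protocol". The same section assigns fasting blood tests to Mayo laboratories. No section says where second-site patients attend CR, have the cardiopulmonary exercise test (CPET) or give blood.

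**The concern.** The single-center label does not fit a recruitment plan with a second health system. The allocation factors, the primary model and the testing locations all read as if there were one centre.

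Two of the three arms, CON and CON+, are delivered through a centre-based programme. If second-site patients attend their own centres, the comparator itself may vary by site, and outcomes may also differ because the populations differ. When site is neither balanced nor modelled, any difference in site mix between arms passes straight into the estimated treatment contrast. For HOM+ against CON the result is read against a fixed margin, so even an accidental shift matters to some degree. The question is how large it could be.

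The testing locations raise a separate, practical question. VO2peak is the Aim 2 primary outcome, and the plan gives second-site staff no instruction on where to obtain it.

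**Working it through.** The plan states no expected second-site share, no site effect and, in the supplied text, no SD or power. There is therefore no figure of its own to reproduce on this point. Its related arithmetic is consistent: 10% of 28 is 2.8, and the Table 4 milestones give 50 + 95 + 94 + 94 = 333, or 15.0, 28.5, 28.2 and 28.2%, as stated after rounding.

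**Inputs**
- From the documents: 333 / 3 = 111 per arm; margin 2.8 mL/min/kg.
- Assumed: second-site share p of 10, 20, 30 or 50%; difference D in adjusted VO2peak between sites of 1, 2 or 3 mL/min/kg.

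**Step 1: chance imbalance.** With no balancing on site, the between-arm difference in second-site share has mean zero and SD = sqrt(2p(1 − p)/111). At p = 20% this is sqrt(0.32/111) = 5.4 points, so the 95% range is ±1.96 × 5.4 = ±10.5 points.

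**Step 2: effect on the contrast.** Shift = (difference in share) × D. At p = 20% and D = 3, an imbalance at the 95% limit gives 0.105 × 3 = 0.32 mL/min/kg, and 0.32 / 2.8 = 11% of the margin.

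| Share p | 95% range (points) | Chance of more than 10 points | Shift at the limit, D = 1 / 2 / 3 | % of margin |
|---|---|---|---|---|
| 10% | ±7.9 | 1.3% | 0.08 / 0.16 / 0.24 | 3 / 6 / 8 |
| 20% | ±10.5 | 6.3% | 0.11 / 0.21 / 0.32 | 4 / 8 / 11 |
| 30% | ±12.1 | 10.4% | 0.12 / 0.24 / 0.36 | 4 / 9 / 13 |
| 50% | ±13.2 | 13.6% | 0.13 / 0.26 / 0.39 | 5 / 9 / 14 |

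The 111 counts every enrolled patient. Surgical patients do only the walk test (section 3.4), so if they are part of the 333, fewer have VO2peak and the ranges widen by sqrt(111/n), where n is the number analysed per arm.

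**Step 3: does balancing on the listed factors already control site?** Minimisation was simulated with 333 patients, 300 runs and a biased coin of 0.8. The assumed minority share was 50% at the second site and 15% at Mayo; only the second figure is in the documents, for Rochester. With the four listed factors, the 95th percentile of the absolute difference in second-site share was 10.0 points at p = 20% and 10.8 at p = 30%. Adding site as a fifth factor reduced these to 2.6 and 2.7. Balancing on race therefore controls site very little.

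**Step 4: scale of a missing CPET, for illustration only.** Non-inferiority power with a true difference of zero is Φ(2.8 / (SD × sqrt(2/n)) − 2.24), where 2.24 is the normal quantile for one-sided 0.0125. If VO2peak were lost in 20% of patients (assumed), n falls from 111 to 88.8 per arm. Power then falls from 89% to 81% at an assumed SD of 6, and from 77% to 66% at an assumed SD of 7.

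**The case against.** The strongest defence is that randomisation already protects the comparison. Each patient is allocated individually among all three arms, so the expected imbalance in site is zero, and over repeated allocations the model's standard error largely allows for it. This stands. A reader might infer that arm is confounded with programme, but the documents do not support that.

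A reader might also be struck by counts within a small second site. Under simple 1:1:1 allocation of an assumed 30 patients there, the chance that CON and HOM+ differ by a factor of 1.5 or more is 40%, and by a factor of 2 or more 16%. Those figures describe a ratio of counts under a method the trial does not use. In terms of the outcome, with 30 such patients the 95th percentile of the share difference is 8.1 points, which at D = 3 is a shift of about 0.24 mL/min/kg, or 9% of the margin.

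Two further points in the plan's favour are fair. No section says that second-site participants attend a different programme: CON and CON+ are defined uniformly, and where those participants attend CR is not stated. And recruitment there is only as needed, so the share may be small or nil.

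On testing, a reader might infer that second-site patients will miss the CPET because distance heads the barriers in Table 2. That table concerns attendance at CR, whereas the trial has three paid assessment visits. The text neither provides for nor rules out travel to Mayo or testing elsewhere, and a single laboratory is a defensible choice for standardisation. What stands is the gap in the instructions, not a demonstrated loss of data.

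**Conclusion.** The inconsistency is real: a trial labelled single-center recruits at a second site, and site appears in neither the allocation factors nor the stated Aim 2 model. The consequence is chance imbalance of modest size. Under the assumed shares and site effects, an imbalance at the 95% limit moves the contrast by about 0.1–0.4 mL/min/kg, 3–14% of the margin. That would matter only if the result lay close to the margin, but it is nearly free to remove.

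The size rests on 111 analysed patients per arm and on assumed shares and site differences. Section 3.7 refers detailed methods to a Statistical Design and Power section that is not in the supplied text, so a site term may already exist there. The unstated testing location is a separate point for reconciliation; any loss of VO2peak through travel is an inference and is not part of this conclusion.

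**What to change.** 1. Add site (Mayo versus University of Minnesota) to the factors in the existing dynamic allocation algorithm, and list it both in section 3.3 and in section 3.7.
2. Include site as a covariate in the Aim 2 ANCOVA alongside baseline VO2peak. This also covers any patients allocated before the algorithm is changed.
3. Replace the single-center description in section 3.3 with two-site.
4. Reconcile section 3.5 with section 3.4: state where second-site patients have blood tests and where non-surgical second-site patients have the CPET, with each patient tested in the same laboratory at every visit. Whether testing is central or local is the sponsor's choice. Local testing would add some between-laboratory variation and needs a suitable laboratory, which the documents do not mention.

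The cost of items 1 to 3 is one more minimisation factor, one degree of freedom and a wording change. A two-level factor does not separate individual CR locations within either health system; it addresses the main division that the documents describe.

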## Description of Comparators

### 1) *Conventional Center-Based CR (CON):*

Participants will be prescribed 36 sessions of center-based CR. This includes supervised exercise sessions, cooking demonstrations, didactic lectures, video presentations, group support, and stress management education. During sessions, participants have direct access to the medical director, case manager, registered nurse, exercise physiologist, and stress management specialists.

### 2) *Conventional Center-Based CR + mHealth (CON+):*

Participants will be prescribed 36 sessions of center-based CR (as noted above). This includes supervised exercise sessions, cooking demonstrations, didactic lectures, video presentations, group support, and stress management education. During sessions, participants have direct access to the medical director, case manager, registered nurse, exercise physiologist, and stress management specialists.

In addition, participants will be provided access to the mHealth platform which provides “e-Learning modules” with factsheets, videos, quizzes, and questionnaires (coinciding with activities being conducted during the CON program), a Social Network Module will allow patients to communicate via a secure network with other patients who are part of their invited network. The Social Network Module also allows for secure two-way interaction with healthcare providers if patients are experiencing signs or symptoms suggestive of worsening condition.

Participants will be given a blood pressure cuff and scale with which they are asked to measure their blood pressure and weight. The device setup will be performed onsite or at home (via video visit after shipping devices to the participant’s address). This data will be uploaded to the mHealth Personal Health Record Module. This module allows patients to upload, archive, and retrieve personal health data (e.g. fitness tracker data, heart rate monitor data, blood pressure recordings, etc.) and record vital signs, symptoms, treatments, and medical history.

